Patient-reported Adverse Events From Osteopathic Manipulative Treatment

Study Protocol and Statistical Analysis Plan

NCT02386085

07/10/2014

PATIENT-REPORTED ADVERSE EVENTS FROM OSTEOPATHIC MANIPULATIVE TREATMENT

STUDY PROTOCOL

A prospective observational cohort study design will be used to accomplish the specific aims of the proposed study. Patients receiving OMT at one of the research sites will receive a coded information packet inviting them to participate in the study. Patients will have the option of completing the 24-hour, 72-hour, and 1-week survey either electronically or using the paper surveys included in the information packet. The clinician will provide documentation of the diagnoses, osteopathic technique(s) used, and body region(s) treated for all patients who complete the 24-hour survey.

i. Participants

DO-Touch.NET members will be recruited to join the proposed study as a research site. The goal is to have at least 50 clinicians contributing to this study. All patients from the research sites who receive OMT and who are age 18 years and above will be eligible to participate in the proposed study. Patients who are unable to communicate in English, Spanish, French, German, or Portuguese will be excluded. Participation is voluntary and informed consent will be elicited from eligible patients prior to their completion of the surveys. A total of 1000 participants will be included in the study.

ii. Recruitment and Procedures

An informational poster will be placed in the waiting room to introduce the study to the patients being seen that day. Following completion of their office visit, eligible patients will be provided an informational packet with a unique code number, paper copies of the surveys, and instructions on how to access the online survey. The code will be recorded by the staff on a tracking sheet to facilitate linking the patient-reported data on adverse events with the clinic treatment documentation.

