Patient-reported Adverse Events: Basic demographic information (i.e., sex, age, race, and ethnicity) will be obtained from participants at the beginning of the 24-hour survey. The 24- and 72-hour surveys will assess the severity, duration, and location of potential adverse events including pain or discomfort, stiffness, unexpected tiredness or fatigue, headache, light headedness, numbness or tingling, muscle weakness, difficulty talking, vision disturbance, tinnitus, nausea or vomiting, problems sleeping, irritability or crying, and difficulty walking. Participants will also be able to add other potential adverse events to the list. They will be asked to assess whether the symptom is definitely, probably, possibly, unlikely, or not related to the OMT received. Additionally, the 24- and 72-hour surveys will assess the existence of these symptoms within the week prior to treatment and whether the participants have sought urgent care, visited the emergency room, or been hospitalized. The 1-week survey will follow-up on adverse events reported on the 72-hour survey. The timing of these surveys is designed to provide information regarding whether the onset of adverse events after OMT is immediate (<24 hours) or delayed (24-72 hours) and whether the duration is short (<72 hours), medium (≥72 hours but less than 1 week), or long (≥1 week).

Documentation of OMT: Documentation of the OMT provided will consist of a standard matrix of checkboxes designating which osteopathic technique(s) were used in which body region(s). The potential osteopathic techniques include articulatory/still, balanced ligamentous tension/ligamentous articular strain, osteopathy in the cranial field, counterstrain/facilitated positional release, high velocity/low amplitude (thrust), indirect/functional method, muscle energy, myofascial release, soft tissue, and visceral. An area will be provided to describe techniques used which are not included in any of these technique groupings. The standard 10 body regions (head/face, neck, thoracic, ribs, lumbar, sacrum, pelvis, abdomen/other, upper extremities, and lower extremities) will be included in the matrix. For each region treated, the physician will be asked to quantify the patient's response to treatment as resolved, improved, unchanged, or worsened.

STATISTICAL ANALYSIS PLAN

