The de-identified data will be downloaded from the REDCap system at the end of data collection. The incidence of each adverse event will be estimated from the entire sample using 95% confidence intervals obtained by fitting generalized linear mixed models to account for the clustering of responses from patients treated by the same clinician. Additionally, generalized linear mixed models will be used to test whether certain techniques or body regions have higher incidence of adverse events than others.

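### The plan describes the pre-treatment symptom item as presence in the prior week only, so a worsened or new-site symptom cannot be reliably separated from a persisting complaint

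*Combined protocol and SAP*

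**What the plan says.** Section iii (Data Collection Instruments, Patient-reported Adverse Events) sets out what patients report after treatment: "The 24- and 72-hour surveys will assess the severity, duration, and location of potential adverse events including pain or discomfort, stiffness", followed by a longer symptom list that also includes headache, numbness and weakness. For the period before treatment, the same paragraph says only that the 24- and 72-hour "surveys will assess the existence of these symptoms within the week prior to treatment".

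No survey comes before treatment. Section ii says: "Following completion of their office visit, eligible patients will be provided an informational packet with a unique code number". The prior-week answer is therefore recalled, and it is the only patient-reported baseline described.

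The plan collects other data that bear on the question:

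- Patients are asked to "assess whether the symptom is definitely, probably, possibly, unlikely, or not related to the OMT received".
- The opening paragraph of the protocol says: "The clinician will provide documentation of the diagnoses, osteopathic technique(s) used, and body region(s) treated for all patients who complete the 24-hour survey".
- Section iii adds, under Documentation of OMT: "For each region treated, the physician will be asked to quantify the patient's response to treatment as resolved, improved, unchanged, or worsened".

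The Statistical Analysis Plan then states: "The incidence of each adverse event will be estimated from the entire sample". It does not say how prior symptoms, severity, location, relatedness or the clinician's rating enter the definition of an adverse event.

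**The concern.** The two halves of the instrument do not match. Pain, stiffness and headache overlap with the complaints for which adults plausibly seek OMT, so many participants may report the symptom for the prior week. That is an inference; the documents give no figure. For these participants, presence alone leaves three situations looking alike: the old complaint continues, it has become worse, or the symptom has appeared in a different place. A single episode some days before the visit is also recorded as present in the prior week.

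The outcome of the study depends on this distinction. Counting every post-treatment symptom includes persisting complaints. Counting only symptoms absent in the prior week drops every aggravation and every new-site symptom in patients who already had that symptom. Adjusting for the item does not help, because it carries no information on change. The technique and region tests use the same outcome. If clinicians tend to treat the regions that hurt, persisting pain could make a region look harmful.

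The problem is greatest for pain, stiffness, headache, numbness and weakness. For symptoms that are rare before treatment it is small, and for symptoms such as nausea or tinnitus the new-site part hardly applies.

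**Working it through.** **What each planned item can and cannot show**

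| Item | What it shows | What it does not show |
|---|---|---|
| Prior-week item | symptom present or not, recalled | severity, site, change |
| Relatedness rating | patient's view of cause | change from before treatment |
| Post-treatment location | where the symptom is now | where it was before |
| Diagnoses and treated regions | what was treated | every site that already hurt |
| Clinician response rating | change per treated region | change per symptom, untreated regions, or (as no later reassessment is described) onset after the visit |

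No row gives change per symptom from before treatment.

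**Size, by illustration**

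The plan has no figure to reproduce: the 1000 participants come without a rate or a precision target. All the rates below are assumptions.

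- q = share with the symptom in the prior week: 30% to 90%
- p = share of those who report it after treatment: 30% or 50%
- r = new onset among the rest: 10%
- w = share of the recurring reports that are truly worse or at a new site: unknown

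Incidence of new, worse or new-site symptoms = (1 − q)r + qpw. Without knowledge of w, it lies between (1 − q)r (w = 0, prior symptoms excluded) and (1 − q)r + qp (w = 1, all counted). The width is qp, whatever the value of r.

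| q | p | Prior symptoms excluded | All counted | Width (points) |
|---|---|---|---|---|
| 30% | 30% | 7.0% | 16.0% | 9 |
| 30% | 50% | 7.0% | 22.0% | 15 |
| 50% | 30% | 5.0% | 20.0% | 15 |
| 50% | 50% | 5.0% | 30.0% | 25 |
| 70% | 30% | 3.0% | 24.0% | 21 |
| 70% | 50% | 3.0% | 38.0% | 35 |
| 90% | 30% | 1.0% | 28.0% | 27 |
| 90% | 50% | 1.0% | 46.0% | 45 |

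For q = 70% and p = 50%, the value is 3.0% + 35% × w. With w = 10%, 30% or 50% this gives 6.5%, 13.5% or 20.5%.

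**Comparison with sampling error**

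Half-width of a 95% interval = 1.96 × √[π(1 − π) × DEFF / 1000], where π is the rate and DEFF = 1 + (m − 1) × ICC. With the goal of 50 clinicians, m = 1000/50 = 20. This approximates the mixed-model interval.

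- No clustering: 1.9, 2.8 and 3.1 points at rates of 10%, 30% and 50%.
- Assumed ICC of 0.10, DEFF = 1 + 19 × 0.10 = 2.9: 3.2, 4.8 and 5.3 points.

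Even the full interval at the assumed ICC is at most 2 × 5.3 = 10.6 points wide, so seven of the eight widths exceed it. The closest case is q = p = 30%: at 16% the full interval is 2 × 1.96 × √(0.16 × 0.84 × 2.9/1000) = 7.7 points, against 9. With a rarer prior symptom the order reverses: q = 20% and p = 30% give 0.20 × 0.30 = 6.0 points, against 2 × 1.96 × √(0.14 × 0.86 × 2.9/1000) = 7.3 points at the all-counted rate of 0.80 × 10% + 6% = 14%.

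**The case against.** A reader might infer that worsening and new-site symptoms cannot be identified at all in this study and that no later analysis could recover them. The documents do not support that, for three reasons.

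1. The relatedness rating is already collected. A patient whose pain rose sharply after OMT and one whose old pain simply continues can answer it differently. Counting symptoms rated at least possibly related is a third option between the two extreme counts, and it needs no new data.
2. Post-treatment location can be linked by code to the diagnoses and treated regions. Neck pain in a patient with only a lumbar diagnosis could often be recognised as new. The clinician's rating also has a category for a region that got worse.
3. The survey forms are not in the document. Presence only is how the plan summarises the item; the form may ask more.

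These points stand and limit the claim. They do not remove it. Relatedness is a judgement of cause, not of change. The clinician's rating is made per treated region, and Section ii ties it to the documentation of that encounter, so nothing shows that it covers onset at 24 to 72 hours. Diagnoses need not list every painful site. The SAP assigns none of these data a role.

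A reader might also take the percentages above as the expected error. They are not: no rate in the documents supports any one of them. Nor is the count of new, worse and new-site symptoms the same as the count caused by OMT, since it includes natural fluctuation in a study without a control group.

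**Conclusion.** The concern holds in this form: the plan describes no pre-treatment severity, no pre-treatment location and no question on change, so worsening or a new site cannot be reliably separated from a persisting complaint by means of the prior-week item. The other planned data are partial proxies without a stated use.

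Under the assumed rates, incidence is left open over 9 to 45 percentage points. In those scenarios this exceeds the sampling error, and a larger sample would not reduce it. The figures rest on 30% to 90% of patients having the symptom beforehand and on 30% to 50% of those reporting it again; for symptoms that are rare before treatment the effect is minor. The range also ignores whatever the proxies could contribute.

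This should be fixed, because it affects the main outcome and the remedy is cheap. It does not show that the data would be unusable without the change.

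**What to change.** **Surveys.** Keep the prior-week item. For each symptom ticked at 24 and 72 hours, and for each location where location has meaning, add: *Compared with just before this treatment, is it new / worse / about the same / better?* Add the severity just before treatment, on the scale used after treatment. If the forms already hold these items, the protocol need only say so.

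**SAP.** For the incidence estimates and the technique and region models, count a symptom as an adverse event if it is new, worse or in a new location. Report symptoms that are the same or better separately, as persisting complaints. Also report the results by relatedness rating.

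**If the forms cannot be changed.** State in the SAP how location, diagnoses, treated regions, relatedness and the clinician's rating will together define an adverse event, and show the count with and without prior-week symptoms as the two limits.

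**Cost.** One or two conditional items in the REDCap and paper forms, and a short definition in the SAP. The surveys become slightly longer, and the comparison still relies on one to three days' recall.

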Informed consent will be obtained as the first page of the 24-hour survey and will include consent for the clinician who treated the patient to provide de-identified documentation of the OMT provided. Participants completing the 24-hour survey online who provide their email address will receive an automated invitation to complete the 72-hour and 1-week surveys. Participants who choose to complete the surveys on paper will be provided a postage-paid envelope to return the surveys to the central coordinating center. Participants who complete all 3 surveys will receive \$10 in the form of a gift card or money order.

When a participant completes the 24-hour survey online or when a completed survey packet is received, the network manager at the central coordinating center will inform the research site that they need to provide documentation of the OMT from the corresponding patient-encounter including the diagnoses treated with OMT, what techniques were performed on that patient, and the clinician's assessment of patient response to the treatment.

iii. Data Collection Instruments

Study data will be collected and managed using REDCap electronic data capture tools hosted at A.T. Still University. Data from participants that is submitted using paper surveys will be entered into REDCap at the central coordinating center.

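### As described, urgent-care, emergency-room and hospital use is asked about only at 24 and 72 hours, so the last 96 of 168 hours of follow-up have no item on it

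*Combined protocol and SAP*

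**What the plan says.** In the protocol, section iii (Data Collection Instruments), the paragraph on patient-reported adverse events divides the content between the surveys as follows.

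- **24- and 72-hour surveys, symptoms.** They "will assess the severity, duration, and location of potential adverse events", and ask how far the participant attributes each symptom to the OMT, on a five-level scale.
- **24- and 72-hour surveys, care use.** The same two surveys ask "whether the participants have sought urgent care, visited the emergency room, or been hospitalized". No recall period is given.
- **1-week survey.** "The 1-week survey will follow-up on adverse events reported on the 72-hour survey". No other content is listed.

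Section ii (Recruitment and Procedures) gives the routes to the later surveys. Online: "Participants completing the 24-hour survey online who provide their email address will receive an automated invitation to complete the 72-hour and 1-week surveys". On paper, everything is handed over at the visit: "eligible patients will be provided an informational packet with a unique code number, paper copies of the surveys". A \$10 payment depends on full completion: "Participants who complete all 3 surveys will receive" it.

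The Statistical Analysis Plan covers the incidence of each adverse event and comparisons of techniques and body regions, both by generalized linear mixed models. It mentions neither care use nor the follow-up of individual events.

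**The concern.** Care use is the one described item that directly captures serious consequences of an adverse event. If the surveys follow the description, it stops at 72 hours although a survey is already planned at 1 week. A participant whose symptom began on day 2 and who went to an emergency room on day 5 would have no described place to report the visit. A participant with no event at 72 hours has no described question at 1 week at all.

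A smaller gap sits beside it. The 1-week survey is tied to what was reported at 72 hours. Someone who reports an event at 24 hours, skips the 72-hour survey and answers at 1 week has no described follow-up of that event.

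What is at stake is the completeness of descriptive safety data. A statement about care use built from the described items could cover only 72 hours.

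**Working it through.** The plan gives no figure of its own on this point, so there is nothing to reproduce. The inputs from the documents are the survey times (24 hours, 72 hours, 1 week) and the planned 1000 participants. I assume that surveys are completed at their nominal times, and that the 24- and 72-hour items together cover the period from OMT to 72 hours.

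**1. Uncovered time.**
- Follow-up: 7 × 24 = 168 h.
- Last described care-use item: 72 h.
- Uncovered: 168 − 72 = 96 h, and 96/168 = 0.571, or 57%.

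**2. What that could mean for users missed.** Let F(t) be the proportion with a first care use by time t. The documents give no rates, so I bound the result instead of estimating it. If the rate of first use does not rise after OMT, F is concave with F(0) = 0, so:
- F(168) ≤ (168/72) × F(72) = 2.33 × F(72).
- Share of first users missed = 1 − F(72)/F(168) ≤ 1 − 72/168 = 0.571.
- The share is 0 if all first use falls within 72 h.
- Put as counts, for every 3 users recorded by 72 h, between 0 and 3 × 96/72 = 4 more go unrecorded.

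The upper end needs a constant rate over the week. Care unrelated to OMT would behave that way.

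**3. Illustration with a hypothetical zero count.** Suppose none of 1000 participants reports care use by 72 h.
- One-sided 95% upper limit for 72 h: 1 − 0.05^(1/1000) = 0.00299, or 0.30%.
- Carried to 1 week at a constant rate: 1 − (1 − 0.00299)^(168/72) = 0.00697, or 0.70%.
- If a 1-week item had also been asked and found none, the limit for the whole week would be 0.30%.

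This ignores clustering by clinician and dropout, and 0.70% is again the constant-rate end.

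**4. Skipping only the 72-hour survey.** The number affected is 1000 × (share with a 24-hour event) × (share skipping only the 72-hour survey). Both shares are assumptions.
- 10% and 1%: 1000 × 0.10 × 0.01 = 1.
- 50% and 5%: 1000 × 0.50 × 0.05 = 25.
- 50% and 30%: 1000 × 0.50 × 0.30 = 150.

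The result follows the assumed rates almost entirely. It also counts events already over by 24 hours, which need no follow-up. I therefore claim no size for this part.

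**5. After the change.** With a care-use item at 1 week that reaches back to the last completed survey, the uncovered time falls from 96 of 168 h to 0 of 168 h for those who answer.

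**The case against.** **The point rests on a short description.** The forms are not in the documents, and following up an event could include asking about care sought for it. This stands as a limit: no item described is not the same as no item. Even on that reading, though, the question would reach only people with an event reported at 72 hours.

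**The scope may be deliberate.** The surveys are timed to show "whether the onset of adverse events after OMT is immediate (<24 hours) or delayed (24-72 hours"), so capture of new events closes at 72 hours and the 1-week survey serves persistence. That explains why new symptoms are not sought at 1 week. It does not explain leaving out late care for a symptom that began by 72 hours.

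**A question put to everyone will pick up unrelated care, and the cohort has no comparator.** This is correct. The plan asks about relatedness for symptoms, not for care use, so a bare count would be hard to read. The fix therefore adds a relatedness question.

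**Not everyone has a described contact at 1 week.** Also correct: the automated invitation goes only to online responders who give an email address. Paper users already hold the forms, and no later contact is described. The added item reaches those who answer.

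**The skipped-survey gap is narrow.** The symptom list is repeated at 72 hours, so a persisting event is normally reported again. The payment for all three surveys discourages skipping, and a paper 1-week form cannot be pre-filled from 72-hour answers, so it may well be generic. All of this stands. What remains is a sentence that, read literally, leaves such a person out.

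**Conclusion.** The point holds as a minor one. As described, care use from 72 to 168 hours, 96 of 168 hours, has no item. How many users this would miss is unknown: from 0% to at most 57% of first users in the week, provided the rate does not rise after OMT. The hours assume nominal completion times; a 72-hour survey completed late would narrow the gap.

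Three stronger readings are tempting, and the documents do not support them.

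- **That 57% of care use will be lost.** That figure is the share of hours, and it bounds the share of users only under a constant rate. Nothing in the documents makes it the expected loss.
- **That the planned results are compromised.** The incidence estimates and the technique and body-region tests use neither care use nor the 1-week follow-up of individual events.
- **That the duration classes cannot be assigned because no starting point is stated.** The cut-points are the survey times, and counted from OMT all three classes can be assigned. Saying that they measure persistence after OMT would be a useful clarification of wording, but it is not part of this finding.

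**What to change.** 1. On the existing 1-week survey, paper and online, ask every respondent about urgent-care, emergency-room and hospital use since the last survey they completed, and whether they think it was related to the OMT. The five-level scale already used for symptoms would serve.
2. Change the follow-up sentence so that the 1-week survey covers events reported on the 24- or the 72-hour survey that had not resolved.

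No extra contact is needed. The costs are a slightly longer 1-week form, some more paper data entry, and revision of the paper, REDCap and any translated forms. Some care unrelated to OMT will be recorded; the relatedness question helps in reading it but does not remove it.

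### Onset, and duration beyond 72 hours, lean on survey timing that the plan neither controls nor records, so events may be put in the wrong timing class undetected

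*Combined protocol and SAP*

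**What the plan says.** Section iii of the Study Protocol (Patient-reported Adverse Events) gives the reason for having three surveys: "The timing of these surveys is designed to provide information regarding whether the onset of adverse events after OMT is immediate" or delayed, and how long events last. Onset has two classes, under 24 hours and 24 to 72 hours. Duration has three: under 72 hours, 72 hours to under 1 week, and 1 week or more.

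The same paragraph says what the forms ask. "The 24- and 72-hour surveys will assess the severity, duration, and location of potential adverse events", along with relatedness, symptoms in the week before treatment, and urgent, emergency or hospital care. It lists no item on when a symptom began. The last form has a narrower role: "The 1-week survey will follow-up on adverse events reported on the 72-hour survey".

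Section ii (Recruitment and Procedures) sets out delivery and return:

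- After the visit, "eligible patients will be provided an informational packet with a unique code number, paper copies of the surveys" and directions for reaching the online version.
- "Participants who choose to complete the surveys on paper will be provided a postage-paid envelope to return the surveys to the central coordinating center". The centre asks the site for treatment documentation once the filled-in packet arrives.
- Automated invitations to the two later surveys go to people who answered the first one online and gave an email address. No paper reminder is described.
- "Participants who complete all 3 surveys will receive" $10. No condition on timing is attached.

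The Statistical Analysis Plan covers the incidence of each adverse event and comparisons by technique and body region. It does not mention the onset or duration classes.

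**The concern.** A survey's nominal hour can stand in for the time of an event only if the survey is answered near that hour, and if the analyst can tell when it was not. The documents describe nothing that secures either condition. A paper participant holds every form from the day of treatment, is not said to be prompted, sends the forms back together and is paid for completing the set. Online access details are also handed out at the visit, and nothing described stops anyone answering the 24-hour survey early.

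There is a separate difficulty with duration, which remains even if every form is filled in on time. Presence of a symptom at a given survey shows how long after treatment it was there. It shows how long the symptom lasted only if the start is known.

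At stake is whether the study can describe events as immediate or delayed, and as brief or lasting. That is the stated reason for the three-survey schedule, and start and completion times cannot be reliably recovered once data collection ends.

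**Working it through.** The plan gives no figure to reproduce on this point, so the check is a reading of the text followed by arithmetic.

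**1. Onset: which way can it go wrong?**

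- *Early completion, either mode.* The 24-hour form is filled in at hour t, with t below 24. An event starting between t and 24 hours is truly immediate but can first appear on the 72-hour form, where it looks delayed.
- *Late or all-at-once completion, mainly paper.* The 24-hour form is filled in at or after 72 hours. An event that started between 24 and 72 hours may be entered on it and look immediate.

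The two errors run in opposite directions, so without recorded times the net bias cannot be signed. A joint return misclassifies nothing in itself, but it removes the receipt date as a check on each form. Paper data are keyed in at the coordinating centre, so the entry date does not help either.

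**2. Onset: how large could the second error be?** The documents give no inputs, so every value here is an assumption. Let

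- s = share of respondents on paper, 0.25 to 0.75
- q = share of paper 24-hour forms filled in at or after 72 hours, 0.1 to 0.5
- r = share of those late respondents who do not answer as of 24 hours, 0 to 1
- d = true share of events that are delayed, 0.1 or 0.3

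with equal event rates in the two modes. Then:

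- Share of truly delayed events recorded as immediate = s × q × r
- Observed immediate share = (1 − d) + d × s × q × r

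| Case | s × q × r | Observed immediate share, d = 0.3 (true 70%) | Observed immediate share, d = 0.1 (true 90%) |
|---|---|---|---|
| r = 0 | 0% | 70% | 90% |
| Middle: 0.5 × 0.3 × 0.5 | 7.5% | 72.25% | 90.75% |
| Highest: 0.75 × 0.5 × 1 | 37.5% | 81.25% | 93.75% |

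The effect can be nil or material, and nothing in the documents says which. The table leaves out early completion, which pulls the other way.

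**3. Duration, with every form on time.** Take 1 week as 7 × 24 = 168 hours and an event that starts in the delayed range and is still present at the 1-week survey.

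- Start at 72 hours: 168 − 72 = 96 hours so far.
- Start at 24 hours: 168 − 24 = 144 hours so far.

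The whole range, 96 to 144 hours, lies in the medium class (72 to under 168 hours). Presence on the 1-week survey, taken alone, points to the long class. Such an event may go on to become long, but that is not known at the time of the survey.

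At the 72-hour survey the same event has lasted at most 72 − 24 = 48 hours. Here the direct duration question can put the matter right. The 1-week survey is described only as follow-up and is not said to ask duration.

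**The case against.** The strongest reply is that duration does not depend on the schedule alone: the 24- and 72-hour forms ask for it. That stands. A reader might infer that all three duration classes are read off the survey's nominal time, and the text does not support this. The direct answers cover events that end by 72 hours. What they cannot do is separate medium from long for an event still going on at 72 hours.

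Secondly, the protocol gives a rationale for the schedule and not a classification algorithm. Nothing says that an event must be classed by the form on which it appears. That also stands, and it means that recorded completion dates would help. The survey forms are not in the documents and may already carry such dates or an onset question. If they do, what remains is to state how the answers are used.

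Thirdly, participants may answer on time, may answer for the period named on the form, or may go online. A reader might infer that paper events will be wrongly classed, or that paper participants' timing data are worthless. The documents support only that misclassification may happen and would go unseen.

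Finally, one could say that duration here is meant as persistence to a given time after treatment. The classes would then be coherent, but they would need to be named and reported as persistence.

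**Conclusion.** The concern holds, with limits. As described, the plan has no means of confirming that a survey was answered near its nominal time and no direct question on when a symptom began. Immediate and delayed onset may therefore be confused in either direction without detection. The size is not fixed by the documents: for delayed events recorded as immediate, the assumed inputs above give anything from 0% to 37.5%, and they illustrate the range without estimating it.

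The duration point needs no assumption about behaviour. It is limited mainly to events ongoing at 72 hours, and it applies if presence at 1 week is taken as the measure of long duration.

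A reader might go further and conclude that the incidence estimates or the technique and region comparisons are compromised. The documents do not support that, because neither analysis is described as using these classes. No comparison of paper with online answers is planned either. The effect is on the descriptive onset and duration purpose. The change is worth making because it is cheap now and the information cannot be reliably recovered later.

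**What to change.** 1. Record the date and time of treatment, and ask for the completion date and time on every form, paper and online.
2. For each symptom, ask when it began (hours after treatment). On all forms, including the 1-week form, ask when it ended or whether it is still present.
3. State in the SAP that onset and duration are classified from those answers and not from which survey reported the event.
4. Repeat the onset and duration tables, by survey mode, using only surveys completed within a window around the nominal time that is fixed in advance.

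Separate prepaid envelopes for the paper forms are optional. A postmark shows when a form was posted, so it is only a weak check on when it was completed.

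The cost is a few fields per form and a short addition to the SAP. The forms become slightly longer, reported start and end times carry some recall error, and some surveys drop out of the sensitivity table.
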